6.1 Study treatment

It is our expectation that because of the short exposure to everolimus (a total of 5 days only), the well described everolimus related toxicities will not develop.

However, following discussions with the company (Novartis), two dose levels will be evaluated: a starting dose of 5 mg po daily, will initially be evaluated in a cohort of 3 patients.

For the purpose of this trial, dose-limiting toxicity (DLT) is defined as an everolimus-related grade 3 or higher AE.

Toxicity will be graded based on the Common Terminology Criteria for Adverse Events (CTCAE) Version4.03.

(<http://www.hrc.govt.nz/sites/default/files/CTCAE%20manual%20-%20DMCC.pdf>)

As mentioned, we will start treating enrolled patients on the lower dose level.

-If no DLT occurs, will proceed with dose escalation to the full FDA-approved dose (10 mg po daily).

-If 1 DLT occurs, cohort will be expanded to additional 3 patients; and if another DLT occurs in this expanded cohort no escalation to full dose(10 mg po daily) will be attempted, and cohort will be expanded to 10 patients. If no additional DLT occurs in the expanded cohort, dose escalation to full dose (10 mg po daily) will follow.

-If 2 DLT occur, no escalation to full dose (10 mg po daily) will be attempted, and cohort will be expanded to 10 patients.

As a result of these possibilities, total number of patients included in this phase 0, proof of principle trial can range from a minimum of 10 to a maximum of 16 total patients.

All dosages prescribed and dispensed to the patient and all dose changes during the study must be recorded.

Medication labels will comply with US legal requirements and be printed in English. They will supply no information about the patient. The storage conditions for Everolimus will be described on the medication label.

Everolimus is supplied by Novartis. Everolimus is formulated as tablets for oral administration of 2.5mg, 5mg, and 10mg strength. Tablets are blister-packed under aluminum foil, which should be opened only at the time of administration as drug is both hygroscopic and light-sensitive. Refer to label for expiration date and storage conditions.

The extent of absorption of everolimus through topical exposure is not known. Therefore, IRB NUMBER: PHXB-17-0072-70-15
IRB APPROVAL DATE: 07/03/2018

caregivers are advised to avoid contact with suspensions of Afinitor Tablets. Wash hands thoroughly before and after preparation of either suspension.

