Impact: Reduction in saliva production and oral dryness can have a devastating effect on oral health that potentially leads to malnutrition and poor quality of life. Common palliative therapies for xerostomia include oral lubricants, saliva substitutes, and saliva stimulants (gum, pilocarpine). Unfortunately, these therapies are short-lived and have not consistently demonstrated the ability to relieve xerostomia symptoms. Therefore these patients are left with very few options and this research could provide a long-term solution for these individuals.

This research project brings together a newly-formed, diverse, interdisciplinary team to solve this complex problem. This team takes advantage of the expertise at both Banner – University Medical Center and St. Joseph's Hospital and Medical Center and the ability to recruit patients in Phoenix and Tucson. It extends the mouse model work conducted by the [name] lab to a phase 0 “proof of principle” clinical trial.

Rapamycin derivatives exhibit considerable similarities in mechanism of action constituting a drug class effect. Therefore, this trial is proposing the use of everolimus due to the ease of administration (orally), which we postulate will have similar biological effects as CCI-779. If successful, the opportunity to expand to a randomized, placebo-controlled, double-blind clinical trial is envisioned.

3 Objectives and endpoints

Initial Objective

Document the safe everolimus dose (5 mg versus 10 mg) to be used in the post radiation or chemoradiation setting for salivary function restoration, using a 3 + 3 design.

Once the safe dose has been defined:

Primary Objective

To describe the recovery of salivary gland function after administration of a 5-day course of everolimus, administered two weeks after completion of radiation or chemoradiation therapy

Primary endpoint

The primary end point of the analysis will be the percent recovery of salivary gland function, with pre-everolimus treatment saliva flow rate as the denominator and the saliva flow rate at 3 months after completion of radiation or chemoradiation therapy as the numerator.

Secondary Objectives

- To describe the decrease of saliva flow rates during radiation or chemoradiation therapy
- To describe the changes in saliva protein composition during radiation or chemoradiation therapy and following administration of a 5-day course of everolimus

Secondary endpoints

Secondary endpoints will be:

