4.1 Description of study design

Patients treated with curative intent either in the post-operative or definitive setting with high dose radiotherapy (≥ 50 Gy) with or without chemotherapy will be eligible. There will be one treatment group with each patient serving as their own control. Patients would have their salivary output measured before radiotherapy, 3 weeks after the start of radiotherapy, and at the end of radiotherapy (6 weeks). Patients who demonstrate more than a 50% decrease in

saliva flow rates will enter the treatment phase of the trial. Based on expert experience, we estimate that half the treated patients will exhibit a decrease of 50% or more in flow rate. These affected patients will then receive the planned dose of everolimus **once a day for 5 days, starting two weeks after the completion of radiotherapy**. Salivary output measurements will be obtained prior to everolimus administration and at completion of the 5 day everolimus course and at 1 month, 3 months and 6 months after the completion of radiation or chemoradiation therapy.

It is our expectation that because of the short exposure to everolimus (a total of 5 days only), the well described everolimus related toxicities will not develop.

However, following discussions with the company (Novartis), two dose levels will be evaluated: a starting dose of 5 mg po daily, will initially be evaluated in a cohort of 3 patients.

For the purpose of this trial, dose-limiting toxicity (DLT) is defined as an everolimus-related grade 3 or higher AE.

Toxicity will be graded based on the Common Terminology Criteria for Adverse Events (CTCAE) Version4.03.

(<http://www.hrc.govt.nz/sites/default/files/CTCAE%20manual%20-%20DMCC.pdf>)

As mentioned, we will start treating enrolled patients on the lower dose level.

-If no DLT occurs, will proceed with dose escalation to the full FDA-approved dose (10 mg po daily) [in this case, total number of patients in the trial: 13; 3 in the 5 mg cohort, 10 in the 10 mg cohort].

-If 1 DLT occurs, cohort will be expanded to additional 3 patients; and if another DLT occurs in this expanded cohort, no escalation to full dose (10 mg po daily) will be attempted, and cohort will be expanded to 10 patients [in this case, total number of patients in the trial: 10; all in the 5 mg cohort];

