- 9) If the patient is too dry, (dry mouth), it is possible to add the weight of the gum base to the pre-weight measure with the gum base in the cup of saliva.

Analysis of saliva: The collection tubes are weighed before and after saliva collection. The difference equates to the total mL collected which is divided by the number of minutes of collection. Saliva is stored at -80°C for further analysis on salivary protein composition at a later date (described in correlatives below).

The comorbidity of mucositis is an important consideration in this study due to the development of this condition following radiotherapy and as a side effect from chronic use of everolimus. Treatment with everolimus has been designed to begin two weeks after radiotherapy to allow radiation-induced mucositis to start improving. In a pre-clinical model,

concurrent rapamycin treatment with radiotherapy (6Gy/day X 5 days) prevents mucositis due in part to increased expression of mitochondrial superoxide dismutase (MnSOD) (Iglesias-Bartolome 2012). Given the short duration of treatment in this trial (5 days), a delay in the start of everolimus until two weeks after radiotherapy and evidence from this pre-clinical study, we postulate that mucositis will not be a major concern. Patients will be closely monitored for worsening mucositis response once treated with everolimus and if mucositis worsens in 2 out of the first 6 patients, then everolimus 50% dose reduction will be implemented.

5 Population

Patients with locally advanced squamous cell carcinoma of the head and neck, treated with curative intent either in the post-operative or definitive setting with high dose radiotherapy (≥ 50 Gy) with or without chemotherapy will be eligible. Patients will be stratified for exploratory analyses in the analysis phase on the basis of ipsilateral vs bilateral neck irradiation. There will be one treatment group with each patient serving as their own control.

This study will evaluate the response in 10 – 16 patients enrolled at both facilities: St. Joseph's Hospital and Medical Center in Phoenix and Banner – University Medical Center in Tucson (details and justification of sample size in statistical methods) to determine if the proposed everolimus dosing schedule of 5 days is sufficient to show recovery of salivary gland function to pre-treatment levels.

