As a result of these possibilities, total number of patients included in this phase 0, proof of principle trial can range from a minimum of 10 to a maximum of 16 total patients.

Maximum number of 16 patients will occur if a DLT occurs in one of the first 3 patients in the 5 mg cohort, and no DLT occurs in the additional 3 expanded cohort patients (for a total of 6 patients in the 5 mg cohort). Subsequently, 10 additional patients will be enrolled in the 10 mg cohort, for a maximum total of 16 patients.

Planned analyses will be performed by strata (patients enrolled at the 5 mg dose level versus the 10 mg dose level).

Statistical analysis will compute the mean percent recovery of all treated patients (with a 95% confidence interval). Ten patients at the selected dose will allow estimating the mean percent recovery with standard error that is 0.32 of the observed standard deviation. Exploratory analysis will determine if any clinical factors are predictive of treatment response, specifically ipsilateral vs bilateral neck irradiation. Changes in the secondary endpoints across time, including the saliva flow rates, saliva protein composition, total score obtained on the Xerostomia Inventory survey, and total score on the Xerostomia Visual Analog Scale survey, will be explored using graphical methods.

10 Protocol amendments, or changes in study conduct

Any change or addition (excluding administrative) to this protocol requires a written protocol amendment that must be reviewed by Novartis and the investigator before implementation. Amendments significantly affecting the safety of subjects, the scope of the investigation or the scientific quality of the study require additional approval by the IRB at each study center. A copy of the written approval of the IRB must be provided to Novartis. Examples of amendments requiring such approval are:

1. increases in drug dose or duration of exposure of subjects,
2. significant changes in the study design (e.g. addition or deletion of a control group),
3. increases in the number of invasive procedures,
4. addition or deletions of a test procedure required for monitoring of safety.

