All subsequent monitoring visits will consist of randomly selected subject cases based on current enrollment and include continuing review of previously selected cases, as applicable.

A monitoring visit report and follow-up letter will be completed approximately two weeks after the routine monitoring visit; a copy will be maintained in the study file. The monitor will request additional source documentation, clarification, information, or corrections to the CRF and/or regulatory records from the Clinical Research Coordinator (CRC) or other applicable staff responsible for the study and resolution of queries/findings. Documentation of such a request will be maintained with a copy of the monitor's visit report for follow-up at the next monitoring visit. Electronic records will be available in the institutional database or provided by the QA/QC Program staff.

The Principal Investigator will ensure the accuracy, completeness, legibility and timeliness of the data reported in the Case Report Form (CRF), or other acceptable data formats. Source documentation supporting the study data should indicate the subject's participation in the trial and should document the dates and details of study procedures, adverse events, and patient status.

All Case Report Forms (CRF) will be entered into the institutional database and completed electronically.

Note: Routine monitoring of regulatory documents will be conducted at least every six months, and routine monitoring of test article will be conducted at least every three months.

11.4 Process to implement study closure when significant risks or benefits are identified:

Please see section 9.1 for escalation and de-escalation procedure which may include study closure as determined by occurrence of dose limiting toxicities.

11.5 Plan for assuring data accuracy and protocol compliance:

Routine study activity and safety information will be reported to the DSMB on a monthly basis, or more frequently if requested. These reports will include:

- Study activity, cumulative and for the period under review;
- Safety (narrative description on non-serious and serious adverse events, protocol pre-determined early stopping rules for safety or treatment-emergent adverse events);
- Predetermined protocol early stopping rules for efficacy/futility;
- Status of study in relationship to stopping rules;
- Current dose level of study agent;

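### At 5 mg, the DLT counts that bar 10 mg also order the cohort filled to ten; no DLT rule rejects 5 mg or pauses accrual, and the closure procedure cited in 11.4 is not in 9.1

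*Protocol*

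**What the plan says.** Section 3 sets the initial objective: "Document the safe everolimus dose (5 mg versus 10 mg) to be used in the post radiation or chemoradiation setting", by a 3 + 3 design. The primary objective follows under the lead-in "Once the safe dose has been defined".

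The rule appears in Sections 4.1, 6.1 and 9.1 with the same content. A DLT is a grade 3 or higher adverse event related to everolimus, and "a starting dose of 5 mg po daily, will initially be evaluated in a cohort of 3 patients". The branches at 5 mg are:

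- No DLT in three: escalate to 10 mg and treat ten patients there.
- One DLT in three: "If 1 DLT occurs, cohort will be expanded to additional 3 patients; and if another DLT occurs in this expanded cohort, no escalation", and the 5 mg cohort is filled to ten. If the next three have no DLT, escalate.
- Two DLTs: "If 2 DLT occur, no escalation to full dose (10 mg po daily) will be attempted, and cohort will be expanded to 10 patients".

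The trial total, the protocol says, "can range from a minimum of 10 to a maximum of 16 total patients".

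Section 11.4, on study closure, reads: "Please see section 9.1 for escalation and de-escalation procedure which may include study closure as determined by occurrence of dose limiting toxicities". Section 11.5 has the DSMB receive monthly reports that include the study's status against stopping rules. Section 4.1 also contains one cohort-level trigger that is not DLT-based: "if mucositis worsens in 2 out of the first 6 patients, then everolimus 50% dose reduction will be implemented".

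**The concern.** In a 3 + 3 design, two DLTs in three or in six patients normally count against the dose at which they occurred. Here they count only against the next dose up, and the protocol's response is to enrol more patients at the dose that caused them. Every DLT count with a written branch ends with ten patients at either 5 mg or 10 mg, so the rule has no outcome in which 5 mg is found unsafe. The primary objective presupposes a safe dose, yet these branches go on to it without one having been shown.

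The patients have just completed treatment given with curative intent. An investigator or DSMB member who needs a closure rule is sent by Section 11.4 to Section 9.1 and finds only escalate-or-expand branches, with neither de-escalation nor closure. The DSMB is to be told the study's status against stopping rules but has no DLT count to apply.

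**Working it through.** **The plan's own figures.** The branch totals are 3 + 10 = 13, 10, and 6 + 10 = 16, which gives the stated range of 10 to 16. The precision factor in 9.1 is 1/√10 = 0.316, stated as 0.32. All reproduce. The minimum of ten also confirms that no early stop was built in.

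**Inputs.** The first cohort is three patients, with three more after one DLT and a fill to ten after either barring count (4.1, 6.1, 9.1). The true DLT rate p at 5 mg is not given, so 10%, 20%, 33% and 50% are assumed. Another DLT in the second three is read as one or more.

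**Chance of a written expansion branch.**

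- A = P(exactly 2 of 3) = 3p²(1−p)
- B = P(1 of 3) × P(at least 1 of next 3) = 3p(1−p)² × [1 − (1−p)³]

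For example, at p = 0.20: A = 3 × 0.04 × 0.80 = 0.096; B = 0.384 × (1 − 0.512) = 0.187; A + B = 0.283.

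**Further patients and DLTs.** After 2 of 3, the fill to ten doses 10 − 3 = 7 more. After the six-patient branch it doses 10 − 6 = 4 more. Expected further patients per trial = 7A + 4B, and expected further DLTs = p(7A + 4B).

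| Assumed p | A | B | A + B | Further patients | Further DLTs |
|---|---|---|---|---|---|
| 0.10 | 0.027 | 0.066 | 0.093 | 0.45 | 0.05 |
| 0.20 | 0.096 | 0.187 | 0.283 | 1.42 | 0.28 |
| 0.33 | 0.219 | 0.311 | 0.530 | 2.78 | 0.92 |
| 0.50 | 0.375 | 0.328 | 0.703 | 3.94 | 1.97 |

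**Three of three.** This has no literal branch; its probability is p³. If it is handled like 2 of 3, each such trial also adds seven patients:

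| Assumed p | p³ | A + B + p³ | Further patients | Further DLTs |
|---|---|---|---|---|
| 0.10 | 0.001 | 0.094 | 0.46 | 0.05 |
| 0.20 | 0.008 | 0.291 | 1.48 | 0.30 |
| 0.33 | 0.036 | 0.566 | 3.03 | 1.00 |
| 0.50 | 0.125 | 0.828 | 4.81 | 2.41 |

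These are averages over all trials, including those that never reach a barring branch.

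**How much the counts show.** Exact (Clopper-Pearson) 95% intervals are 9% to 99% for 2 of 3 and 4% to 78% for 2 of 6. Neither count establishes that 5 mg is unsafe, and neither supports calling it safe. That argues for a pause and review rather than either automatic termination or automatic continuation.

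**The cross-reference.** Section 11.4 places a de-escalation procedure and possible closure for DLTs in 9.1. Section 9.1 contains the three branches, the totals and the analysis paragraph. Neither item is there.

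**The case against.** The strongest reply is that the branch is deliberate and other safeguards surround it. The same rule is written out three times, twice with worked totals, for a marketed drug given for five days at half the approved dose. Section 10 says approval requirements must not prevent immediate action for patient safety, and 11.6 provides for suspension. The DSMB has rated the trial high risk, weekly calls cover adverse events and cohort management (11.2), and serious adverse events go to the DSMB (8.2.2). Tables 6-1 and 6-2 take individual patients off drug for most grade 3 or 4 toxicities. The mucositis trigger needs no grade 3 event, and stomatitis heads the list of common grade 3/4 reactions in 8.1.1. That section puts each such reaction at 1% to under 10%, so the 33% and 50% scenarios look high.

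Part of this stands. The authority to act exists, harm per patient is limited, and at a 10% rate the expected excess is only 0.05 DLTs per trial. The further patients and DLTs are counted against stopping outright, so they are upper bounds on what a pause would avoid. Two DLTs may well be read as at least two, which makes the three-of-three gap mainly one of wording.

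None of it supplies the missing rule. The safeguards are discretionary and state no DLT count, while the written rule directs continuation. Taking one patient off drug does not stop the next from being dosed. The mucositis trigger covers one toxicity, and it shows that 2 of 6 was accepted there as grounds for cohort-level action. Low expected toxicity affects how often the branch is reached, not what it orders.

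**Conclusion.** The point holds and should be fixed before the rule is used. Followed as written, the protocol keeps dosing new patients at 5 mg after counts it treats as too toxic for escalation, cannot answer its own safe-dose objective in the negative, and cites a closure procedure that does not exist. In a trial that reaches a barring branch, seven further patients are dosed after 2 of 3 and four after the six-patient branch. How often that happens rests entirely on assumed DLT rates: 9% of trials at a true rate of 10%, rising to 70% at 50%. If toxicity is as low as the protocol expects, the practical effect is small; the branch exists for the case where that expectation fails. A dose-finding rule set out in full in the protocol is not a detail to be left to a separate analysis plan. The conclusion concerns the 5 mg branches only.

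**What to change.** In Sections 4.1, 6.1 and 9.1:

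1. Word the branch as two or more DLTs, so that three of three is covered.
2. In both barring branches, replace the automatic fill to ten with a pause in accrual and DSMB review before any further patient is dosed. Whether 5 mg continues, a lower dose is tried or the trial closes is for the sponsor and the DSMB.
3. State that a 5 mg cohort reaching these counts has not met the Section 3 safe-dose objective. Its recovery data would be descriptive, as the primary objective already is.
4. Correct the minimum total of ten, since the trial could then end after three or six patients.

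Make Section 11.4 point to this rule.

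The cost is a protocol amendment, which may need IRB approval at each centre under Section 10. The DSMB already receives monthly reports. In these branches the trial may end with fewer than ten evaluable patients. Patients register before radiotherapy and are dosed at day 15 after it, within one day either way (Table 7-1), so a pause could make some already in radiotherapy miss their dosing window. The amended rule should say what happens to them.

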6.1.1 Dosing regimen

The investigator should promote compliance by instructing the patient to take the study drug exactly as prescribed and by stating that compliance is necessary for the patient's safety and the validity of the study. The patient should be instructed to contact the investigator if he/she is unable for any reason to take the study drug as prescribed.

Everolimus should be administered orally once daily at the same time every day, either consistently with or consistently without food.

Tablets

The tablets should be swallowed whole with a glass of water and should not be chewed or crushed. For patients unable to swallow tablets, the tablet(s) should be dispersed completely in a glass of water (containing approximately 30 mL) by gently stirring until the tablet(s) is fully disintegrated (approximately 7 minutes), immediately prior to drinking. The glass should be rinsed with the same volume of water and the rinse completely swallowed to ensure the entire dose is administered.

If vomiting occurs, no attempt should be made to replace the vomited dose. Patients should be instructed that if they miss a dose on one day, they must not take any extra dose the next day, but instead to immediately contact the study center as soon as possible to ask for advice.

